### **6.1 INTENT-TO-TREAT POPULATION**

Patients whose primary eyes were randomized to receive either Bim SR or SLT treatment will be referred to as randomized patients. The intent-to-treat (ITT) population is defined as all randomized patients, and will be referred to as “ITT population” in this SAP and

TFLs. Analyses using the ITT population will be based on the randomized treatment assigned to each eye.

The modified intent-to-treat (mITT) population is defined based on ITT population, but will exclude patients who could not receive the second implant due to the discontinuation for the Bim SR 15µg dose strength implemented in [protocol Amendment 3](#). The exclusion algorithm is as follows:

- If a patient had a missing Cycle 2 Day 1 Bim SR administration date with study exit date after March 19, 2020 (IWRS deactivation date), unless the patient had AE leading to drug withdrawn or received a rescue medication before March 19, 2020 in planned Bim SR eye, then the patients will be excluded from the mITT.

The reason for a missing Cycle 2 Day 1 Bim SR administration date is only due to the discontinuation for the Bim SR 15µg dose strength in protocol Amendment 3, not due to AE leading to drug withdrawn or rescue medications.

The mITT population will be used for the primary analysis.

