## 6.2 PER-PROTOCOL POPULATION

The per-protocol (PP) population is defined as all patients in ITT population who have no protocol deviations affecting the data for the primary efficacy analysis for all visits (Week 4, Week 12, and Week 24) in both eyes, and will be referred to as the “PP population” in this SAP and TFLs.

Since the primary eye and contralateral eye of a patient will contribute data separately for the two different treatments in the study, the data from one eye can be excluded from PP analysis due to a protocol deviation, but the patient can still be included in PP population because of valid data from the other eye.

Examples of protocol deviations that will result in removal of data from PP analysis include but are not limited to the following cases:

- For eyes with no study treatment, post-baseline data will be excluded from PP analysis, and
- For eyes that received both study treatments, data after the wrong treatment will be excluded from PP analysis.

A separate document will be prepared to describe data exclusion algorithm for PP analysis. All patients with data excluded from the PP analysis will be identified and

finalized prior to each database lock and will be displayed in a data listing with reason(s) for exclusion.

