#### **10.1 PRIMARY EFFICACY ANALYSIS**

The primary efficacy variable is Hour 0 IOP change from baseline (follow-up value minus baseline value, thus negative values reflect IOP reduction from baseline) assessed at Weeks 4, 12, and 24. Intraocular pressure values at Hour 0 at Baseline visit is considered as the baseline values.

Baseline and Weeks 4, 12 and 24 Hour 0 IOP measurements with their changes from baseline will be descriptively summarized.

Primary efficacy analysis will be performed for patients in the mITT population. The null and alternative hypotheses for the comparison between Bim SR treated eyes and SLT treated eyes at Weeks 4, 12, and 24 are:

- Null hypothesis: the difference in mean IOP change from baseline between the Bim SR and SLT eye (Bim SR minus SLT) is  $> 1.5$  mmHg.
- Alternative hypothesis: the difference in mean IOP change from baseline between the Bim SR eye and SLT eye (Bim SR minus SLT) is  $\leq 1.5$  mmHg.

Hour 0 IOP change from baseline will be analyzed using a mixed effect model for repeated measurement (MMRM). The model will include Hour 0 IOP change from baseline as the response variable and treatment, visit, eye, baseline Hour 0 IOP, treatment-by-visit, treatment-by-baseline Hour 0 IOP, treatment-by-eye, visit-by-eye interactions as covariates. Unstructured covariance matrix for study visit and compound symmetry correlation for eyes will be used for repeated measures on the same patient. If the model fails to converge, alternative covariance structures may be used in the MMRM analysis. If the model fails to converge with alternative covariance structures, multiple imputation (MI) will be implemented before MMRM.

The mean difference in the Hour 0 IOP change from baseline between the Bim SR eyes and SLT eyes (Bim SR minus SLT) in the mITT population and the corresponding 95% confidence intervals (CI) will be constructed at each visit from MMRM analysis. The noninferiority comparison for Bim SR versus SLT at Weeks 4, 12, and 24 is the primary analysis. If the upper limit of the 95% CI is  $\leq 1.5$  mmHg at all 3 visits, Bim SR 15  $\mu$ g statistical noninferiority to SLT is considered demonstrated.

For additional clinical consideration, Bim SR is considered clinically noninferior to SLT if the upper limit of the 95% CI is  $\leq 1.0$  mmHg at 2 out of the 3 visits of Weeks 4, 12, and 24.

Sample SAS® code for primary analysis is shown as below:

```
proc mixed data=iop4;
  where avisitn >1;

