**10.3 OTHER EFFICACY ANALYSES**

#### 10.4 SENSITIVITY ANALYSES

As part of the sensitivity analyses, the mean difference and 95% CI in the IOP change from baseline between the Bim SR eyes and SLT eyes (Bim SR minus SLT) will be constructed for each analysis visit for the Per Protocol (PP) population using the same MMRM model as the one used in the primary analysis.

To simplify the interpretation of treatment effect, and to allow flexible adjustment for baseline effect and the between-eye correlation across different visits, the following MMRM model will be used in sensitivity analysis using mITT population: (1) the MMRM model will include Hour 0 IOP change from baseline as the response variable and treatment, visit, eye, baseline Hour 0 IOP, treatment-by-visit, visit-by-baseline Hour 0 IOP, and visit-by-eye interactions as covariates; (2) an unstructured covariance matrix (6×6 matrix) will be used for measurements across 3 primary visits (Weeks 4, 12, and 24) and 2 eyes for the same patients. The same MMRM model will be used in the tipping-point sensitivity analysis described in the later part of the section.

Sample SAS® code for the sensitivity analysis is shown as below:

```
proc mixed data=iop4;
  where avisitn >1;
  class subjid eye trt avisitn repid;
  model chg=trt avisitn eye base trt*avisitn
        avisitn*base avisitn*eye/ddfm=kr;
  repeated repid/type=un subject=subjid rcorr;
  lsmeans trt*avisitn/diff;
run;
```

The definitions of variables are:

chg = Hour 0 IOP percentage change from baseline at the primary analysis time points of Week 4, Week 12, and Week 24

avisitn = Programming derived analysis visits at Week 4, Week 12, and Week 24

subjid = Subject ID

eye = Variable to indicate primary eye or contralateral eye

trt = Variable to indicate Bim SR treatment or SLT treatment

base = Baseline IOP

repid=Variable created to identify the repeated measures cross each eye and each visit within a given subject for the unstructured covariance matrix ( $6 \times 6$ ).

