Additionally, ANCOVA including within-subject correlation at each visit will be conducted using the observed values of ITT population, where IOP measurements obtained after initiating the use of non-study IOP-lowering medication will be set to missing. At each visit, the model for IOP change from baseline is specified as: IOP Change from Baseline = Treatment + Eye + Baseline IOP, where Eye is primary eye or contralateral eye. A compound symmetric covariance matrix will be used for between eye correlation.

The tipping-point sensitivity analysis will also be used to assess the robustness of the analysis results. A multiple imputation (MI) will be performed to the missing data as the first step; then different shifts using various assumptions on the missing IOP CFB will be applied to the imputed missing values in Bim SR treated eyes separately (note: shift will not be applied to SLT treated eyes); finally MMRM analyses will be conducted based on the imputed data with shifts and the corresponding tipping region of the shifts will be used to evaluate the robustness of the noninferiority conclusion.

In the MI procedures, a two-step method will be used to impute the missing values at Weeks 4, 8, 12, 15, 20, and 24 for each eye. During Step 1, missing intermittent data will be imputed to obtain a monotone missing pattern and during Step 2 linear regression will be used to impute the remaining missing values. Note that baseline IOP values associated with each eye must not be missing in any of the patients; otherwise they will be excluded from this analysis. At least twenty-five (25) sets of imputed datasets will be created using SAS proc MI procedure. A sample code is shown below for Hour 0 IOP measurements associated with each eye:

```
proc mi data=iop nimpute=25 seed=123451 out=_miint;  
  var baseline week4_hr0 week8_hr0 week12_hr0 week15_hr0 week20_hr0 week24_hr0;  
  by treatment;  
  mcmc chain=single impute=monotone;  
run;  
  
proc mi data=_miint nimpute=1 seed=123457 out=mifull;  
  class race_group sex lens;  
  var race_group sex lens age baseline week4_hr0 week8_hr0 week12_hr0 week15_hr0 week20_hr0  
  week24_hr0;  
  monotone regression (week4= race_group sex lens age baseline/details);  
  monotone regression (week8= race_group sex lens age baseline week4/details);  
  monotone regression (week12= race_group sex lens age baseline week4 week8/details);  
  monotone regression (week15= race_group sex lens age baseline week4 week8 week12/details);  

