## **16.0 DATA HANDLING CONVENTIONS**

### **16.1 EFFICACY DATA**

As stated in protocol [Section 5.9.1.5](#) Retreatment with Bim SR, when eye(s) received non-study IOP lowering medication or procedure, to avoid confounding of efficacy data, IOP measurements obtained after initiating the use of non-study IOP-lowering medication or procedure in an eye will be treated as missing for that eye.

Additionally, handling of missing data will be supplemented by sensitivity analyses using multiple imputation and tipping point (adding different penalties on the imputed values) approach.

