7. In Section 11.1, analysis of SLT procedure related ocular TEAEs by SOC and PT is added.

8. In Section 16.1, delete the statement below since mITT is covered excluding patients who had one Bim SR implant. Details for mITT is described in Section 6.1.

- ~~• Additionally, for patients treated with Bim SR in Cycle 2, Week 24 data in primary analysis will be treated as missing if Bim SR treatment was not done in Cycle 2.~~

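### The primary mITT drops whole patients for a Week 16 event, which costs usable Week 4 and 12 data, and its date rule does not match its stated intent

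*SAP*

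**What the plan says.** SAP 6.1 builds the mITT from the ITT set "but will exclude patients who could not receive the second implant due to the discontinuation" of the 15 µg strength under Protocol Amendment 3. The algorithm is by patient. A patient with no Cycle 2 Day 1 administration date and a study exit after March 19, 2020 leaves, "unless the patient had AE leading to drug withdrawn or received a rescue medication before March 19, 2020 in planned Bim SR eye". SAP 6.1 then states that a missing Cycle 2 date arises only from the discontinuation.

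SAP 10.1: "Primary efficacy analysis will be performed for patients in the mITT population". That analysis is an MMRM at Weeks 4, 12 and 24, and SAP 10.2 uses the same set for superiority. Protocol 7.1, 7.3.1 and 7.3.2 agree. The Protocol Summary names the ITT population instead.

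Three other provisions bear on the point:

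- **SAP 16.1** already handles rescue eye by eye. IOP after non-study "medication or procedure in an eye will be treated as missing for that eye".
- **SAP 10.4** adds an ITT sensitivity analysis: "ANCOVA including within-subject correlation at each visit will be conducted using the observed values of ITT population". It also adds an MMRM "for the Per Protocol (PP) population using the same MMRM model as the one used in the primary analysis".
- **SAP 6.2** draws PP from ITT but leaves the exclusions open: "A separate document will be prepared to describe data exclusion algorithm for PP analysis".

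**The concern.** The second implant is due at Week 16 (SAP 4.0), and the Week 12 analysis window closes at Day 91 (SAP Table 16-1). Withholding the implant therefore cannot affect two of the three primary visits. Until then these patients had the same planned treatment as everyone else. Dropping them at Weeks 4 and 12 departs from the randomised set where no treatment change calls for it, and it widens the intervals that decide noninferiority.

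An MMRM accepts patients with incomplete visits, so the loss is avoidable. The SAP's change log shows that a visit-level rule was once written: "Week 24 data in primary analysis will be treated as missing if Bim SR treatment was not done in Cycle 2". That text is superseded and is cited only to show that the alternative was workable.

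A second issue is that the algorithm may not do what SAP 6.1 says it does. It tests two dates, not the reason for the missed administration.

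**Working it through.** **Inputs.** SAP 14.0 and Protocol 7.5 give a per-eye SD of 4 mm Hg, between-eye and within-patient correlations of 0.5, a true difference of 0, two-sided 0.05, and 144 evaluable patients. The number excluded is not given. I assume 7, 14 or 29 of 144 (about 5, 10 and 20%).

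**Step 1: reproduce the plan.**

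- SD of the paired difference = 4 × √(2 × (1 − 0.5)) = 4.
- SE = 4/√144 = 0.333.
- Per-visit power at 1.5 mm Hg = Φ(1.5/0.333 − 1.96) = 99.4%.
- Per-visit power at 1.0 mm Hg = Φ(1.0/0.333 − 1.96) = 85.1%.
- Joint power, with visit correlation 0.5: 98.5% (1.5 mm Hg, 3 of 3) and 88.9% (1.0 mm Hg, 2 of 3). The plan states about 98% and 90%, so its figures reproduce.

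**Step 2: whole-patient exclusion.** With m patients left, SE = 4/√m at every visit. For m = 137, 130 and 115 this is 0.342, 0.351 and 0.373.

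**Step 3: keep Weeks 4 and 12 and the SLT eye.** Only the Bim SR eye at Week 24 is missing.

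- Weeks 4 and 12: SE stays at 0.333.
- Week 24: with the visit and eye correlations multiplying, as in the SAP's UN@CS structure, the residual variance of the missing value given the patient's other five is 16/(1.333 × 1.5) = 8. Here 1.333 = 1/(1 − 0.5²) is the eye factor and 1.5 is the diagonal of the inverse 3 × 3 visit correlation matrix.
- So SE = √(8/m + 8/144) = 0.338, 0.342 and 0.354.

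**Step 4: joint power** (2,000,000 draws, baseline ignored; direct evaluation of the normal probabilities agrees within 0.1 point).

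| Excluded of 144 | 1.5 mm Hg, 3 of 3: mITT | Weeks 4/12 kept | 1.0 mm Hg, 2 of 3: mITT | Weeks 4/12 kept |
|---|---|---|---|---|
| 7 | 98.0% | 98.4% | 87.2% | 88.6% |
| 14 | 97.3% | 98.3% | 85.2% | 88.4% |
| 29 | 95.0% | 98.0% | 80.2% | 87.8% |

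Amendment 3 also closed enrolment, so fewer than 144 may be evaluable. As an assumed case, with 100 evaluable and 20 excluded the figures are 81.7% against 89.3% (1.5 mm Hg) and 62.7% against 72.0% (1.0 mm Hg).

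**Step 5: selection through the exceptions.** Late enrollees with Bim SR-eye rescue or AE withdrawal before the cut-off stay in, while other late enrollees leave. Assume 14 late enrollees and a 10% rate of such events. Their share rises from 10% to 144 × 0.10/(130 + 1.4) = 11.0%. If their Bim SR minus SLT difference were 3 mm Hg worse (assumed), the mean would shift by (0.1096 − 0.10) × 3 = 0.03 mm Hg, against Bim SR. Over 7 to 29 late enrollees and rates of 5 to 20%, the shift is 0.01 to 0.12 mm Hg.

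**Step 6: the date rule against its intent.** Protocol 8.10 lets a patient miss an administration visit and stay in the study to Week 52. Week 52 is 36 weeks after Week 16. A patient whose Cycle 2 fell due, and was missed for another reason, up to about 36 weeks before March 19, 2020 can therefore exit after that date. Unless an exception applies, the algorithm removes that patient although Amendment 3 was not the cause.

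**The case against.** The strongest reply is that much of this is already covered. At Weeks 4 and 12 the ITT by-visit ANCOVA uses exactly the data in question, adjusted for eye, baseline and between-eye correlation. The mITT is specified consistently in the body of the Protocol and the SAP, and it keeps one set of patients behind a joint 3-of-3 decision. The alternative relies on a missing-at-random Week 24 response to an implant that was never given.

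The excluded share may also be modest. If accrual had been uniform over the roughly 230 weeks from October 2015, 16/230 is about 7%. Spreading the planned 120 Stage 2 patients over about 110 weeks gives about 17 of 160, or 11%. Both accrual patterns are assumptions. Near 10% excluded, the loss on the 1.5 mm Hg criterion is about one point.

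Most of this stands, and it limits the point to a supportive analysis. Two things remain. The ANCOVA mixes one-implant and two-implant eyes at Week 24, so no visible analysis gives all three visits on ITT with that handled. Whether the PP MMRM keeps these patients depends on a document not included here.

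Two stronger readings are tempting, and the documents support neither. A reader might infer that the exclusion biases the comparison. It follows mainly a calendar date, both eyes leave together, and the outcome-related exceptions shift the mean by an estimated 0.03 mm Hg against Bim SR. A reader might also infer that no ITT MMRM is planned. SAP 10.3 has no visible text, so one cannot be ruled out.

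**Conclusion.** The point holds as an avoidable loss of precision at Weeks 4 and 12, together with an exclusion rule that does not implement its own stated intent. The loss is 0.4 to 3.0 percentage points on the 1.5 mm Hg criterion (98.4 − 98.0 to 98.0 − 95.0) and 1.4 to 7.6 points on the 1.0 mm Hg one (88.6 − 87.2 to 87.8 − 80.2), which SAP 10.1 treats as an additional clinical consideration. These figures rest on 144 evaluable patients, 5 to 20% excluded and the plan's own SD and correlations. The excluded share and the actual enrolment are unknown, and the loss is larger if fewer patients were enrolled. How many patients the date rule wrongly removes cannot be derived. Confining the primary analysis to patients eligible for two implants is defensible, so the mITT need not be replaced as primary. Separately, the Protocol Summary conflicts with the rest of the Protocol and the SAP on which population is primary.

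**What to change.** Before the first database lock:

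1. **Add a named supportive analysis.** Run the primary MMRM on ITT. For patients whose Cycle 2 was withheld by Amendment 3, set only the Bim SR-eye Week 24 IOP to missing, and keep Weeks 4 and 12 and the SLT eye. Making this the primary analysis is optional and would have to be documented as a change made before the lock.
2. **Correct the exclusion rule.** Define it by the recorded reason for the missed Cycle 2, or by whether Cycle 2 fell due after the deactivation date, not by exit date. Report the number excluded.
3. **Name one primary population.** Reconcile the Protocol Summary (ITT) with Protocol 7.1 and 7.3.1 and SAP 6.1 and 10.1 (mITT).

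The cost is one flag, one extra MMRM run and wording changes, with no new data. SAP 13.0 already holds the first lock until all patients reach Week 24 or discontinue, so under the SAP the lock need not move. The downside is reliance on missing-at-random for the affected Bim SR-eye Week 24 values, which is credible because dosing stopped on a calendar date.

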6.5 Summary of Methods of Data Collection

This study will use eCRFs using remote electronic data capture through a qualified third party vendor. The data will be entered on the eCRFs in a timely manner on an ongoing basis. The investigator is responsible for ensuring that data are properly recorded on each patient's eCRFs and related documents. An investigator who has signed the protocol signature page should personally sign for the case report forms (as indicated in the eCRFs) to ensure that the observations and findings are recorded on the eCRFs correctly and completely. A certified electronic copy of the eCRF including data corrections will be provided to the site for archiving at the end of the study.

A central laboratory or designated regional facility will be used for analysis of blood chemistry and hematology, urinalysis, and ocular fluid sample analysis (if ocular fluid is obtained). Laboratory data will be transferred to Allergan on a periodic basis throughout the study.

7. Statistical Procedures

Two database locks will be performed: 1) when patients included in the primary analysis have completed the Week 24 visit or have prematurely discontinued before the Week 24 visit, and 2) when all patients complete the Week 52 visit or exit the study. Analyses will be performed after each lock. Prior to the first database lock a detailed analysis plan will be finalized. To maintain the integrity of the ongoing study, Allergan study personnel who are directly involved in data handling and supporting the trial (such as the clinical study team) will remain masked to treatment assignment of individual patients during the study. To avoid potential data unmasking between locks and to protect trial integrity, study statistical personnel who have been unmasked after each lock will no longer be involved directly in any ongoing masked study conduct. Another statistician, who is still masked to study treatment, will assume these responsibilities until the next lock. Unmasked data handling and appropriate data and results access will be specified prior to each lock.

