8.9 Early Discontinuation of Patients

Patients may voluntarily withdraw from the study at any time.

Patients who have received nonstudy IOP-lowering medication in one or both eyes, or who do not undergo Cycle 2 (or Cycle 3, for Stage 1 patients) administration, will be followed for the duration of the study through the Week 52/Exit visit.

If the implant has been removed, the patient may discontinue the study if based on investigator assessment the eye is in stable condition, at which time they should complete the Week 52/Exit visit procedures.

Notification of early patient discontinuation from the study and the reason for discontinuation will be made to Allergan and will be clearly documented on the appropriate case report form.

When patients discontinue before Week 52/Exit, the site should complete all procedures for the Week 52/Exit visit at the patient's last visit.

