8.10 Withdrawal Criteria

After the first administration (or Sham), failure to undergo an Administration Day visit does not indicate total withdrawal from the study. Patients who have received nonstudy IOP-lowering treatment in one or both eyes, or who do not undergo Cycle 2 (or Cycle 3, for Stage 1 patients) administration will continue through the duration of the study.

The investigator should consider withdrawing a patient from the study early if any of the following criteria are met:

- Patient develops (or has an exacerbation of) a medical condition that, in the opinion of the investigator, compromises the patient's ability to participate in the study
- Patient is unwilling or unable to continue to comply with study procedures
- Patient is unwilling or unable to continue in the study

If a patient develops (or has an exacerbation of) a medical condition that, in the opinion of the investigator, would put the patient at an unacceptable medical risk by continuing study participation, the patient will be withdrawn from the study.

Whenever possible, the decision to withdraw a patient from the study or study treatment should be discussed with Allergan.

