Section 5.9.1.5	Administration of Bimatoprost SR will occur at fixed intervals of 16 weeks, up to a total of 3-2 3-2 administrations (or 3 for Stage 1 patients) unless in the investigator's opinion it would not be in the best interest of the patient to re-administer Bimatoprost SR based on previous adverse events or safety concerns. Patients who have been treated with nonstudy IOP-lowering medication in both eyes will not attend the administration day visits, nor will they attend the Day 2, Day 4 (phone call),	Specified that visits associated with the third treatment cycle are for patients who reached Week 32 prior to implementation of Amendment 2 only and extended safety follow-up period for patients who received nonstudy IOP-lowering medication in both eyes or did not complete an administration visit

Approval Date: 27-Mar-2020

Section	Revision	Rationale
	
and Week 2 (phone call) visits following an administration. Patients who have received nonstudy IOP-lowering medication in only 1 one or both eyes will be followed for the duration of the study through the Week 52/Exit visit. Patients who have received nonstudy IOP lowering medication in both eyes, or who do not complete an Administration Day visit, as described in Section 5.9 will still remain in the study and will be followed for 16 weeks after the last Bimatoprost SR or Sham administration.
	
Section 6.2	
Best Corrected Visual Acuity: Visual acuity tests will be performed at all scheduled visits except on any of the 3 Bimatoprost SR administration days or SLT Administration Day.
	
Removed number of administration visits

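### The mITT rule in SAP 6.1 tests study exit after 19 March 2020, not whether the second implant was still pending, and says nothing about patients without an exit date

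*SAP*

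**What the plan says.** SAP 6.1 states the purpose of the mITT population: it "will exclude patients who could not receive the second implant due to the discontinuation" of the 15 µg strength. SAP 10.1 runs the noninferiority test on this population.

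The algorithm that follows in 6.1 begins "If a patient had a missing Cycle 2 Day 1 Bim SR administration date with study exit date after March 19, 2020" (the day the interactive response system was deactivated). It then spares patients with an adverse event leading to drug withdrawal, or with rescue before that date, in the planned Bim SR eye. The next sentence reads "The reason for a missing Cycle 2 Day 1 Bim SR administration date is only due to the discontinuation" and rules out adverse events and rescue as the reason. It names no data item to test.

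Protocol 7.1 defines mITT with no exit-date criterion. Under Protocol 8.9, patients who do not undergo Cycle 2 "will be followed for the duration of the study through the Week 52/Exit visit", and Protocol 8.10 adds that "failure to undergo an Administration Day visit does not indicate total withdrawal from the study".

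Protocol 7 sets the first lock at the point "when patients included in the primary analysis have completed the Week 24 visit" or have left before it, and says "Prior to the first database lock a detailed analysis plan will be finalized". SAP 5.1 and 13.0 also tie the first lock to Week 24. SAP 19.1 item 8 deletes a former rule that set Week 24 data to missing when Cycle 2 was not given, on the ground that mITT now deals with those patients.

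**The concern.** The definition is about cause and the algorithm is about calendar time. Because missing Cycle 2 does not end follow-up, a late exit date shows only that the patient stayed on study. It does not show that the implant was unavailable when due. The two listed exceptions narrow the proxy but do not cover every other reason for a missed implant. Protocol 12.2.2 records the retreatment rule that applied before Amendment 3, under which the investigator could withhold the implant if "it would not be in the best interest of the patient to re-administer Bimatoprost SR based on previous adverse events or safety concerns". It is cited here only as the rule then in force. A concern of that kind need not be an adverse event coded as leading to withdrawal.

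The rule also needs a field that is blank for anyone still on study at the lock. SAP 10.2 gives a fallback for a missing exit date when censoring time to rescue; 6.1 gives none.

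At stake is who enters the confirmatory test. Protocol 7 also times the first lock by membership of the primary analysis, so membership has to be settled while exit dates may still be blank. With the former Week 24 rule gone, mITT is the only safeguard against one-implant Week 24 data entering the primary model.

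**Working it through.** **Inputs.** SAP Table 16-1, counted from the first implant as Day 1: Week 16 = Day 109, Week 24 = Day 165 (window ends Day 178), Week 52 = Day 361. Protocol 8.4.3.7: Week 16 window -2/+4 days, so Days 107 to 113. Protocol 8.4.3.14: Week 52 window ±7 days. Cut-off: 19 Mar 2020.

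**(a) Available implant, patient excluded.**
- Week 16 to Week 52 is 361 - 109 = 252 days. 19 Mar 2020 minus 252 days is 11 Jul 2019, so Week 16 targets from about that date lead to a scheduled exit after the cut-off.
- The last window that had closed by the cut-off has Day 113 on 19 Mar 2020, so its target (Day 109) is 15 Mar 2020.
- The exposed band is therefore Week 16 targets from about 11 Jul 2019 to 15 Mar 2020.

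Two patients miss an available implant for the same reason, outside the exceptions:

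| First implant | Week 16 | Week 52 | Rule |
|---|---|---|---|
| 15 Jun 2019 | 1 Oct 2019 | 9 Jun 2020 | excluded |
| 15 Feb 2019 | 3 Jun 2019 | 10 Feb 2020 | kept |

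Only the calendar separates them.

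**(b) Blocked patient, no exit date.**
- First implants from 29 Nov 2019 have a Week 16 window still open after the cut-off (Day 113 = 20 Mar 2020). For 29 Nov to 4 Dec 2019 the window spans 19 March.
- The earliest Week 52 in this group is 23 Nov 2020, or 16 Nov with -7 days.
- The latest first implant is taken as 19 Mar 2020 (assumption: none after deactivation). Its Week 24 window ends 12 Sep 2020 and its Week 52 is 14 Mar 2021.
- From 12 Sep to 16 Nov 2020 is 65 days. At a lock in that gap, every blocked patient still on study has a blank exit date and does not meet the exclusion test as written.
- The SAP amendment is dated 29 Sep 2020 and the plan must precede the lock. A lock from then to 15 Nov 2020 would fall in the gap. The actual lock date is not given.

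**Power, plan's figure first.** SD of the paired difference = 4 × √(2 × (1 - 0.5)) = 4 mm Hg. SE = 4/√n. Each visit succeeds if Z ≤ margin/SE - 1.96, with three visits correlated 0.5 and true difference 0. At n = 144, SE = 0.333, giving 98.5% for 1.5 mm Hg at 3 of 3 visits (plan: about 98%) and 88.9% for 1.0 mm Hg at 2 of 3 (plan: 90%). If 10 are wrongly excluded (assumed), n = 134, SE = 0.346, and power is 97.7% and 86.4%.

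**Week 24 shift under (b), assumed.** With k blocked patients kept and their paired difference shifted by d, the simple mean moves by k × d/144: 5 × 1/144 = 0.03 mm Hg up to 10 × 3/144 = 0.21 mm Hg, in either direction.

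**The case against.** The strongest reply to (a) is the sentence on the reason for the missing date. The amendment was written on 29 Sep 2020, after the last Week 16 window had closed (9 Jul 2020 for a first implant on 19 Mar 2020), by authors who knew individual cases: SAP 6.3 describes one patient treated twice in the same eye. If the sentence reports a completed check, (a) is empty. That stands as a possibility. The SAP does not say that a check was made. If the sentence is instead a condition, it contradicts the algorithm for the patients in (a), and it gives the programmer nothing to test.

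On (b), the intent is clear. Anyone still on study at a lock after 29 Sep 2020 will exit after 19 March 2020, and SAP 19.1 item 8 and Protocol 7.1 both point to exclusion. Taken alone, (b) is a wording gap. It still leaves a primary-population rule resting on inference.

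A closed Week 16 window does not prove that the implant was available. SAP Table 16-2 lets the Week 15 window run up to the actual Cycle 2 date, so late administrations were foreseen, and a patient running late on 19 March was truly blocked. This stands, and the remedy must allow for it.

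Other analyses give partial cover: SAP 10.4 has a by-visit ITT ANCOVA and a per-protocol MMRM drawn from ITT. The first is a different model. Whether the second includes these patients depends on a separate exclusion document.

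A reader might infer that patients were in fact misclassified, or that the rule tilts the test towards noninferiority. The documents support neither: they give no counts, no lock date and no basis for a direction.

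**Conclusion.** As written, the algorithm does not implement the definition it serves. It can exclude a patient whose implant was available and, at a Week 24 lock before about 16 Nov 2020, it does not exclude blocked patients still on study. This should be corrected because it fixes membership of the confirmatory population and no backstop remains. The known impact is small: under the plan's assumptions, 10 wrong exclusions cost 0.8 points of power at 1.5 mm Hg and 2.5 points at 1.0 mm Hg. The Week 24 shift of 0.03 to 0.21 mm Hg rests wholly on assumed counts and effects. Part (a) may be empty, and the number affected under either part and the direction of bias cannot be determined from the documents.

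**What to change.** Replace the exit-date test in SAP 6.1 with four conditions, applied whether or not an exit date is recorded:
- no Cycle 2 Bim SR was given;
- the patient was still on study on 19 Mar 2020;
- Cycle 2 was still pending on that date;
- there was no adverse event leading to drug withdrawal, and no rescue, in the Bim SR eye before that date.

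Derive the pending status from the first-implant date and the Week 16 window, using the SLT + 3 days anchor of Table 16-1 if no first implant was given. Before the lock, carry out a masked review of case records for patients whose window spans 19 March (first implants 29 Nov to 4 Dec 2019) and for those whose window had closed shortly before without an administration. List every exclusion with its reason. If the sentence on the reason for the missing date reports a completed check, say so and cite the listing.

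Add one sensitivity analysis: the primary MMRM on all ITT patients, with Week 24 IOP set to missing for those affected by the discontinuation, so that their Week 4 and Week 12 data are kept.

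The cost is SAP wording, one derived flag from dates already collected, a short case review and one model run. The Protocol Summary names ITT for the primary analysis where Protocol 7.3.1 and SAP 10.1 name mITT. That is a separate alignment point and adds no weight here.
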